2. STUDY PROCEDURES

a. Procedures

Screening: Patients who have been recommended to undergo endoscopic sinus surgery by our department will be recruited for the study and informed of its purpose pre-operatively. SNOT22 scores (a quality of life survey well established in Rhinology) and Lund-Kennedy endoscopic exam scores (an quantitative clinical assessment of disease severity) will be recorded in their medical records. This is the same protocol performed for all patients seen in our clinic regardless of their enrollment in the study. Randomization and Treatment Groups: The patients that wish to participate will be randomized into two treatment arms by our nurse practitioner based on a random number generator. They will receive one of the following post-operative regimens: 1) oral steroid (treatment) + steroid spray (treatment) 2) oral placebo (control) + steroid spray (treatment) These medications will be manufactured and packaged by an independent compounding pharmacy, and prescribed by our nurse practitioner at the preoperative visit. Patients will begin their therapy on the first post-operative day. All oral steroid regimens will be given in our institution's standard 12 days taper, while topical steroids will be delivered via a metered dose nasal spray bottle for two weeks. All study patients will receive identical perioperative antibiotic therapy. We do not anticipate these medications to be an inconvenience to study patients as all proposed interventions are not different from routine post-operative care. In addition, patients undergoing surgery will have already trialed these medications as part of their pre-operative medical therapy. Surgery: Routine endoscopic sinus surgery will be performed per our institution's standard protocol. In this step there will be no difference in treatment from those patients not enrolled in the study. Post-Operative Care: At this point, patients will begin therapies according to the treatment arm to which they have been randomized. Study patients will attend post-operative appointments at identical time points to non-study patients. These will take place at the following intervals: Post-operative visit 1: 1-2 weeks Post-operative visit 2: 6-8 weeks Post-operative visit 3: 12-16 weeks Post-operative visit 4: 6 months Experimental therapy will finish after 2 weeks. At this visit, all patients will then be maintained on intranasal steroid spray and nasal saline irrigations, which is the commonly employed therapeutic standard. Thereafter, patients will, per standard protocol, be followed on an observational basis depending on the severity of symptoms and response to treatment. At each visit, as is done for all individuals, SNOT-22 and LundKennedy endoscopic exam scores will be repeated and recorded.

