
b. Procedure Risks

This study does not seek to evaluate a novel research procedure. Rather, we endeavor to determine if a procedure already in place nearly universally is, in fact, beneficial, as there is a

distinct lack of evidence of suggest so. Overall, we are investigating a procedural method that will have fewer side effects than the currently accepted practice.

c. Use of Deception in the Study

NA

d. Use of Audio and Video Recordings

NA

e. Alternative Procedures or Courses of Treatment

All reasonable alternatives are included as a treatment arm in this study. There is no standard of care that is being withheld from patients in any group.

f. Will it be possible to continue the more (most) appropriate therapy for the participant(s) after the conclusion of the study?

Yes, patients will stop all experimental therapies at the 2 week mark. They will then be placed on the typical post-operative regimen, which includes a nasal steroid spray and twice daily saline irrigations. They will continue to be followed in our clinic after the 4 week mark, and their therapies tailored to their current symptoms and the endoscopic appearance of the nasal cavity.

g. Study Endpoint(s)

Currently, our post-operative protocol dictates that patients will be seen in clinic at 1 week, 3 weeks, and 6 weeks after surgery. We will only slightly alter this timeline for study patients. At the 2 week appointment, all experimental therapies will be completed. Patients will then be started on intranasal steroid sprays and saline irrigations so as not to deviate for an extended period from currently accepted practices. We will use the final scheduled appointment at 4 weeks after surgery as the official end point for comparison of treatment arms. Additionally, outcomes evaluated will be the symptom questionnaire and the endoscopic exam score at each visit. If, during the course of follow up, one regimen proves to be clearly superior to another, the study will be terminated and patients will receive the optimal therapy. By power analysis, we require 50 patients to achieve statistical significance. If there is a clearly optimal therapy determined in these first 50 patients, we will end our research at that time. All patients will continue to be followed beyond 4 weeks depending on symptom severity and response to treatment

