5. PARTICIPANT POPULATION

a. Planned Enrollment

Based on a current rate of 12-15 endoscopic sinus surgeries weekly, as well as allowing for a significant percentage of patients who do not desire to participate in the study, we anticipate between 80 and 100 patients to enroll. The study will be conducted only at Stanford Hospitals and Clinics. Participants will be those with CRS with and without polyps who have been recommended and consented for endoscopic sinus surgery. These participants will be used because they suffer from the specific disease for which we endeavor to research alternative therapies

b. Age, Gender, and Ethnic Background

We will recruit patients >18 that are able to provide consent. There will be no gender or ethnic exclusions.

c. Vulnerable Populations

NA

d. Rationale for Exclusion of Certain Populations

Children will not be included in this study as it is not typical for endoscopic sinus surgery to be performed in this population. It is rare for them to develop the extent of disease that would require surgical intervention, and surgery, in fact, is often avoided as the sinuses have not fully developed in the pediatric population. Furthermore, they are unable to provide their own informed consent to participate in this trial.

e. Stanford Populations

NA

f. Healthy Volunteers

NA

g. Recruitment Details

Recruitment will be invitation only from the patient population seen in our Rhinology clinics. Patients will first be evaluated by our providers. If, based on that evaluation, endoscopic sinus surgery is recommended to them and they meet inclusion criteria, they will then be informed of the study and its purpose and importance. After this has been discussed, patients will be invited to participate if they so choose. Our nurse practitioner performs all study introductions and obtains consent. If there are any questions, Rhinology providers are always available for consultation. We do not intend to advertise to nor recruit within the general public. There will be no recruitment materials.

h. Eligibility Criteria

i. Inclusion Criteria

Age > 18
Able to provide informed consent
Chronic rhinosinusitis with or without nasal polypsis based on published diagnostic criteria
Patients undergoing endoscopic sinus surgery

ii. Exclusion Criteria

Age
Aspirin exacerbated respiratory disease
Allergic fungal sinusitis
Cystic fibrosis
Immunosuppression
Chronic steroid use
Steroid use within 30 days prior to surgery

i. Screening Procedures

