6. RISKS

a. Potential Risks

i. Investigational devices

NA

ii. Investigational drugs

NA

iii. Commercially available drugs, biologics, reagents or chemicals

Oral Prednisone: The side effects of short courses of systemic steroids (<3 weeks) include stomach upset, weight gain, insomnia, hyperglycemia, hypokalemia, adrenal suppression, and mood changes. These can occur in up to 16% of patients, with stomach upset being the most common. These effects are all reversible after stopping the steroid. Topical Fluticasone: The side effects of topical steroids include dry throat, sore throat, nasal irritation, headache, nose bleeds. These are the more common side effects, the incidence of which is unknown. Rare and serious side effects include difficulty breathing, flu symptoms, and vision changes. Again, these typically improve after stopping the steroids. On very rare occasion, vision symptoms may be permanent. None of these interventions differ from those already being instituted by our staff.

iv. Procedures

See the risks of the commercially available drugs - None of these interventions differ from those already being instituted by our staff.

v. Radioisotopes/radiation-producing machines

NA

vi. Physical well-being

NA

vii. Psychological well-being

NA

viii. Economic well-being

NA

ix. Social well-being

NA

x. Overall evaluation of risk

Low - innocuous procedures such as phlebotomy, urine or stool collection, no therapeutic agent, or safe therapeutic agent such as the use of an FDA approved drug or device.

b. International Research Risk Procedures

NA

c. Procedures to Minimize Risk

Medication administration will be monitored during the post-operative visits. Patients will begin their assigned therapy the day after surgery, and then will be seen 1, 2, and 4 weeks post-operatively. Any side effects being encountered will be discussed at these visits, and specialty services available in a timely manner to address them if needed. Furthermore, patients have 24 hour access to a physician in the department, and are, at any time, able to call with questions or concerns regarding their treatment.

Identifiable patient information will be handled per institutional protocol. Unique login information is required for all persons wishing to access the electronic medical system. All communications with patient data are sent on a secured machine via an encrypted service that is password protected.

d. Study Conclusion

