The study will officially terminate for each patient after the 4th post-operative visit.

If a patient is experiencing an adverse outcome from surgery or from post-operative therapy, their participation in the study will be terminated early in the interest of well-being. In this event, patients will be promptly seen in subspecialty clinics (or by inpatient consultants if the patient is

admitted to the hospital) that may assist in managing these complications. Additionally, if a patient is having an emergency, they are able to contact one of our house staff 24 hrs per day for advice. As a last resort, our Emergency Department is available for expedited work up of major events.

Finally, if it becomes clear after the first 50 patients have completed their interventional therapy that one therapy arm is drastically superior to others, and that patients are thus not receiving optimal care, the study will be terminated and therapies altered.

e. Data Safety Monitoring Plan (DSMC)

- i. Data and/or events subject to review

Aggregate Data Analysis Reports Progress toward study endpoints AEs, SAEs, SUSARs

- ii. Person(s) responsible for Data and Safety Monitoring

The Protocol Director will be responsible for Data and Safety Monitoring.

- iii. Frequency of DSMB meetings

NA

- iv. Specific triggers or stopping rules

Currently, our post-operative protocol dictates that patients will be seen in clinic at 1 week, 3 weeks, and 6 weeks after surgery. We will only slightly alter this timeline for study patients. At the 2 week appointment, all experimental therapies will be completed. Patients will then be started on intranasal steroid sprays and saline irrigations so as not to deviate for an extended period from currently accepted practices. We will use the final scheduled appointment at 4 weeks after surgery as the official end point for comparison of treatment arms.

Additionally, outcomes evaluated will be the symptom questionnaire and the endoscopic exam score at each visit. If, during the course of follow up, one regimen proves to be clearly superior to another, the study will be terminated and patients will receive the optimal therapy. By power analysis, we require 50 patients to achieve statistical significance. If there is a clearly optimal therapy determined in these first 50 patients, we will end our research at that time. All patients will continue to be followed beyond 4 weeks depending on symptom severity and response to treatment.

- v. DSMB Reporting

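### The efficacy stopping rule at the first 50 patients has no threshold, deciding score or number of looks, and the SAP omits it; one look at 50 of 75 gives a type I error of 5.01% to 7.7%, depending on the threshold

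*Protocol*

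**What the plan says.** The protocol provides for ending the trial on efficacy in three wordings.

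- Section 2g, at any time: "If, during the course of follow up, one regimen proves to be clearly superior to another, the study will be terminated".
- Section 2g, at a patient count: "If there is a clearly optimal therapy determined in these first 50 patients, we will end our research at that time". The sentence just before it says that a power analysis requires 50 patients for statistical significance. Section 6e-iv, under the heading for triggers and stopping rules, repeats this text.
- Section 6d, which would end the study "if it becomes clear after the first 50 patients have completed their interventional therapy that one therapy arm is drastically superior to others".

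On outcomes, 2g says: "Additionally, outcomes evaluated will be the symptom questionnaire and the endoscopic exam score at each visit". On timing it says: "We will use the final scheduled appointment at 4 weeks after surgery as the official end point for comparison of treatment arms". Neither sentence is tied to the stop. Section 6e makes the Protocol Director the only monitoring entity and enters DSMB meetings as not applicable.

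Section 5a forecasts enrolment: "we anticipate between 80 and 100 patients to enroll". The SAP, dated July 2020 and written in the past tense, gives a planned size of 75 and repeats the 50 from the power analysis. It lists t-tests at each time point for SNOT-22 total and subdomain scores, Lund-Kennedy scores and adverse effects. It mentions no interim look, stopping rule or adjusted level.

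**The concern.** A trial that may stop on a favourable result at 50 patients, and otherwise tests again at 75, has two chances of a false positive. How much that matters depends on how strict the first test is, how many scores can trigger it and how often the data are examined. The protocol leaves all three to judgement, and it provides no independent body that could supply the criterion. The SAP does not say whether the rule was applied. A reader of the final p-values therefore cannot tell whether they need adjusting, or by how much.

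**Working it through.** **The plan's own figure.** The 50 cannot be reproduced, because no effect size, SD, alpha, power or endpoint is given. Under an assumed 1:1 allocation, two-sided 5% and 80% power, the normal approximation d = (1.960 + 0.842) × √(4/N) gives 2.802 × 0.2828 = 0.79 SD for N = 50 and 2.802 × 0.2309 = 0.65 SD for N = 75. These serve below only as assumed effects.

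**Inputs.** Look at 50 (2g, 6d). Final N of 75 (SAP), or 80 and 100 (the ends of the 5a forecast). Assumed, because the documents are silent: two-sided 5% at the final test, 1:1 allocation, one score, one look.

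**One look, one score.** The test statistics at 50 and N have correlation √(50/N): 0.816 for 75 and 0.707 for 100. Type I error = 1 − P(|Z1| ≤ c1 and |Z2| ≤ 1.960), where c1 is 1.960, 2.576 or 3.291.

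| Threshold at the look | N = 75 | N = 80 | N = 100 |
|---|---|---|---|
| p<0.05 | 7.70% | 7.86% | 8.31% |
| p<0.01 | 5.26% | 5.31% | 5.46% |
| p<0.001 | 5.01% | 5.01% | 5.02% |

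Simulated t-tests at N = 75 with a look at p<0.05 give 7.7% with equal arms and 7.8% with unrestricted 50:50 allocation, so exact 1:1 allocation is not critical.

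**What the wording could mean.** With 25 per arm (48 df), the smallest observed difference reaching a threshold is t × √(2/25): 0.57 SD at p<0.05, 0.76 SD at p<0.01 and 0.99 SD at p<0.001. Nothing in the text says which of these would be clear or drastic superiority.

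**More looks.** Adding a look at an assumed 25 patients (one score, N = 75) gives about 10.7% if the looks use p<0.05, 5.9% at p<0.01 and just over 5% at p<0.001.

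**Either score can trigger the stop.** With a look at p<0.05 and one score tested at 75, the error is about 12.3% if the scores are uncorrelated and about 10.1% at a correlation of 0.8. Testing two scores once, with no second analysis, already gives 1 − 0.95² = 9.75% and 7.8% respectively. So 4.75 of the 7.3 points above 5%, or 2.8 of the 5.1, come from having two outcomes.

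**Levels that hold 5% at 50 of 75.** Solving the same expression for the final level gives about 0.047 after a look at p<0.01 and 0.0499 after p<0.001. Equal levels at both analyses are 0.0318 (0.0294 for 50 of 100). Using 0.0318 at the final test after a look known to be at p<0.01 or p<0.001 gives an overall error of about 3.5% or 3.2%, which over-corrects.

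**The case against.** The strongest reply is that the harm is conditional. No alpha, sidedness or threshold is stated, so 7.7% needs a look at ordinary significance. The 6d wording suggests something stricter, and at p<0.01 the excess is only 0.3 points. That stands, and it limits the size of the point. It does not remove the point, because 2g puts its significance sentence directly before the stopping sentence, so a look at p<0.05 cannot be excluded.

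Fifty may also have been the analysable target, with 75 allowing for losses. The documents do not say so. Even on that reading, 2g requires results by arm to be examined in the first 50.

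Four weeks is the natural reading of the comparison time in 2g. That is fair: the gap is that the stop is not tied to it. A reader might go further and infer that 6d moves the comparison to the end of therapy at 2 weeks, against 2g. The text does not support this, since 6d can be read as setting only the earliest time of a look.

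A reader might also take the 10% to 12% two-score figure as the effect of the interim look. More than half of the excess is outcome multiplicity, which is a separate issue.

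**Conclusion.** The concern holds as an unspecified efficacy rule that is missing from the SAP. For one look at 50 of 75 on one score, with an assumed two-sided 5% final level and 1:1 allocation, type I error runs from 5.01% (look at p<0.001) to 7.7% (look at p<0.05); at a final 100 it runs from 5.02% to 8.3%. It is negligible under a strict threshold and material near p<0.05, and more looks would raise it.

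A reader might infer that the data were examined early, or that the reported p-values are inflated. The documents support neither: nothing in them shows that a look took place. What they do show is a standing commitment to stop, with no criterion and no account in the SAP of whether it was used.

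**What to change.** 1. **If data by arm have been examined** (likely, given the SAP's past tense): state in the SAP and report whether, when, on which score and visit, and by what threshold an efficacy look was made. If none was made, say so; no adjustment for looks is then needed. This costs a few sentences and no power.
2. **If one look was made at 50 on one score:** set the final level at 75 from the disclosed threshold, about 0.047 after p<0.01 or 0.0499 after p<0.001. Use 0.0318 at both analyses (0.0294 for 50 of 100) only if the threshold was about p<0.05 or is unknown. At an assumed 0.65 SD, two-stage power with 0.0318 is about 76%, against 79.3% with no look. With more looks, or either score deciding, derive the level from what was done, or report the p-values as not error-controlled.
3. **Only if the data are unexamined:** name one primary score and time point. Replace the efficacy triggers in 2g, 6d and 6e-iv with one look when 50 patients have that score, with a pre-set boundary that holds 5% overall, and put the same rule in the SAP. Two examples for 50 of 75 are p<0.001 then 0.049 (overall 4.9%) and about 0.012 then 0.046 (overall about 5.0%). Both keep power near 79% at 0.65 SD. They differ in the chance of stopping early at an assumed 0.79 SD, about 26% against about 57%, which is the trade-off to decide. A different final number needs a new derivation.

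Leave safety stopping unchanged. No patients are needed beyond the SAP's 75.

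Separately, reconcile the 4-week end point in 2g and the 6c schedule ("Patients will begin their assigned therapy the day after surgery, and then will be seen 1, 2, and 4 weeks post-operatively") with the 2a list, which has no 4-week visit: "Post-operative visit 1: 1-2 weeks Post-operative visit 2: 6-8 weeks".

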Screening will be performed during clinic visits. First, it must be determined if a patient is a surgical candidate, which is a decision based on establishing the diagnosis of chronic rhinosinusitis by published diagnostic criteria. Furthermore, patients with this diagnosis must have failed maximum medical therapy. At the pre-operative appointment, a complete routine history will be taken as is standard in our clinics. This will include information regarding past medical history, past surgical history, current medications, social history, family history, and allergies. This information is readily available to us as a part of the electronic medical record. Patients must also confirm accuracy by filling out a questionnaire prior to their first encounter. No qualifying laboratory values are necessary.

j. Participation in Multiple Protocols

We do not anticipate that participants will be enrolled in more than one study. However, we will be sure to inquire before enrolling patients if they are actively participating in another study. If so, and our interventions may interfere in any way, we will not continue with the enrollment

process. We do not anticipate difficulty in recruiting the required number of patients, and, therefore, will defer to studies in which patients are already enrolled.

k. Payments to Participants

NA

l. Costs to Participants

The participant will accrue identical costs to any patient being evaluated and treated for chronic rhinosinusitis, which will vary tremendously based on insurance policies. During the process, costs that may accumulate include: clinic appointments, prescribed medications, surgical intervention, specialty evaluation. No additional costs will be charged based on participation in this study.

m. Planned Duration of the Study

The study duration is anticipated to be 12 months. Time allotted for screening of the participant will depend heavily on the time that elapses between the initial patient encounter in clinic and the date for which surgery is scheduled. This may require 1-6 months, and occasionally longer. Active study participation will begin at the surgical date and end at the 4th post-operative visit. Organization and analysis of the data will require 2-4 weeks.

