Perioperative Oral Steroids for Chronic Rhinosinusitis Without Polyps

Statistical Analysis Plan

NCT02748070

July 2, 2020

[name], Principal Investigator
Stanford University
Stanford, California 94305

The planned sample size was 75 patients. By power analysis, we required 50 patients to achieve statistical significance. We collected outcome measures of SNOT-22 and Lund-Kennedy endoscopy scores at the following time points: preoperative baseline, and postoperatively at 1 week, 1 month, 3 months, and 6 months.

All statistical analyses were performed using Stata 15 (Stata Statistical Software: Release 15; StataCorp LP, College Station, Texas). SNOT-22 total scores, SNOT-22 subdomain scores, Lund-Kennedy endoscopic scores, and adverse effects were compared between prednisone and placebo groups at each time point using t-tests.

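### The documents conflict on whether the 3- and 6-month assessments are fixed for every patient, and the SAP has no plan for late scores that are missing as a result

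*Protocol*

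**What the plan says.** Some of the text makes the late assessments fixed. Protocol section 2a lists "Post-operative visit 3: 12-16 weeks Post-operative visit 4: 6 months" and states "Study patients will attend post-operative appointments at identical time points to non-study patients". It adds "At each visit, as is done for all individuals, SNOT-22 and LundKennedy endoscopic exam scores will be repeated and recorded". Section 5m says "Active study participation will begin at the surgical date and end at the 4th post-operative visit", and section 6d ends the study for each patient at the same point. The SAP lists 3 and 6 months among its collection times without any condition.

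Other text points the other way. Sections 2g and 6e-iv describe the 4-week appointment as the final scheduled one and make it the official end point for comparing arms. Both then say "All patients will continue to be followed beyond 4 weeks depending on symptom severity and response to treatment". Section 2a, after the visit list and the end of experimental therapy, says "Thereafter, patients will, per standard protocol, be followed on an observational basis depending on the severity of symptoms and response to treatment". Section 6c names visits at 1, 2 and 4 weeks only.

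On analysis, the SAP says that SNOT-22 total and subdomain scores, Lund-Kennedy scores and adverse effects "were compared between prednisone and placebo groups at each time point using t-tests". It defines no analysis set, no handling of missing scores and no repeated-measures model.

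**The concern.** Scores are taken at visits, so a patient with no late visit has no late score. Someone working from 2g or 6e-iv could reasonably treat anything after 4 weeks as clinical follow-up driven by symptoms. Someone working from 2a would book everyone at 12-16 weeks and 6 months. Under the first practice, recovered patients would tend to be missing, and more of them in whichever arm did better. A t-test on the available scores would then understate a true difference between arms.

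The direction matters here. Sections 3a and 7 hope to show that topical treatment works as well as the oral regimen, and shrinkage towards zero favours that conclusion. Losing scores also reduces power, which again makes a real difference easier to miss.

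**Working it through.** **1. The passages side by side.**

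| Place | Late assessments |
|---|---|
| Protocol 2a, visit list | 12-16 weeks and 6 months, unconditional |
| Protocol 2a, later sentence | follow-up depends on severity and response |
| Protocol 2g and 6e-iv | 4 weeks is the last scheduled visit; later follow-up depends on severity and response |
| Protocol 6c | weeks 1, 2 and 4 only |
| Protocol 5m and 6d | participation ends at the fourth visit |
| SAP | 3 and 6 months, unconditional |

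Section 6c names three visits, so a fourth exists only in the 2a list, where it falls at 6 months. Sections 5m and 6d therefore support the fixed reading; 2g, 6c and 6e-iv do not fit it.

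**2. The plan's own figure.** The only figure near this point is the 50 patients required by power analysis. It cannot be reproduced, because alpha, power, effect size and SD are not given. No attendance figure is given either, so everything below is illustration on assumed inputs.

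**3. Attendance depending on the late score itself.** Assume scores normal with SD 20, placebo mean 28 and prednisone mean 28 - d. Call a score below 20 well. Let a be the attendance rate among well patients and b the rate among the others. With z = (20 - mean)/20 and P = Φ(z):

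- attendance = aP + b(1 - P)
- upward shift in the attenders' mean = 20 φ(z)(b - a) / attendance

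For placebo, z = -0.40, P = 0.345 and φ = 0.368. For prednisone with d = 5, z = -0.15, P = 0.440 and φ = 0.394.

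Worked case, a = 0.4 and b = 0.9:
- Placebo: attendance 0.728; shift 20 × 0.368 × 0.5 / 0.728 = 5.06.
- Prednisone: attendance 0.680; shift 20 × 0.394 × 0.5 / 0.680 = 5.80.
- Observed difference: 5 + 5.06 - 5.80 = 4.26.

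| a / b | Placebo mean overstated by | True 5 reads | True 8 reads |
|---|---|---|---|
| 0.80 / 0.95 | 1.23 | 4.89 | 7.86 |
| 0.60 / 0.90 | 2.77 | 4.69 | 7.58 |
| 0.40 / 0.90 | 5.06 | 4.26 | 6.92 |

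The shrinkage runs from about 2% (8 to 7.86) to 15% (5 to 4.26). With d = 0 the two shifts are equal and the between-arm bias is zero.

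**4. Attendance depending on an earlier score.** A second model was simulated: 70% overall attendance, correlation 0.5 or 0.7 between early and 6-month scores, and log-odds of attending rising by 0.5 to 2 per SD of worse early score. A true 0.5 SD is observed as 0.40-0.49, and 0.8 SD as 0.64-0.78. That is the same direction, with about 20% shrinkage at the extreme. The observed difference stays at about zero when there is no true effect.

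**5. Power.** Suppose 50 patients (25 per arm) gave 80% power at two-sided 5%. The standardised difference is (1.96 + 0.84) × √(2/25) = 0.79. With n scores per arm, power is Φ(0.79 √(n/2) - 1.96). Attendance of 90, 80, 70, 60 and 50% leaves about 76, 71, 65, 58 and 51%. If the SAP's planned 75 are enrolled, 50 late scores remain only with attendance of at least 50/75 = 67%.

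**The case against.** The strongest reply is that the documents, read together, already fix the late visits: the 2a list, the rule that study patients attend, scoring at each visit, and the end of participation at visit four. The quoted sentence opens by saying that all patients continue to be followed, so the condition may govern how intensively they are managed. Section 2f supports this: it has patients followed in clinic after 4 weeks, with therapy tailored to symptoms. Moreover, the condition in 2a follows the 2-week point, so taken literally it would make even the listed 6-8 week visit conditional.

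Much of this stands. A reader might infer that the 3- and 6-month comparisons do use a selected, sicker sample. The documents do not support that: nowhere do they say that a recovered patient skips a visit, and they give neither attendance figures nor a direction of selection. The benign reading still sits badly with 4 weeks being called the last scheduled appointment, so the conflict remains for staff to resolve.

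It is also fair to say that the effect is modest. In the step 3 model, a true difference of 5 loses 0.1 to 0.7 points. The standard error with 75 patients and SD 20 is 20 × √(2/37.5) = 4.6, and most of the shift in mean level is common to both arms and cancels. The 15% figure needs only 40% of well patients to attend, which nothing in the documents suggests.

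**Conclusion.** The point holds as a conflict in the text that creates a risk of outcome-dependent missing scores, together with an SAP that has no means of handling it. It is not established that such selection is part of the design or took place.

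If the severity condition were applied, shrinkage of a true difference would be about 2-15% under the assumed attendance rates, and about 20% in the most extreme setting of the second model. There would be no bias if the arms do not differ, so this would not produce false superiority. Loss of power could matter more than the bias. The importance comes from the aim of showing equal effectiveness, which shrinkage and low power both favour.

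Two further inferences should be resisted. The 4-week official end point is not touched by this sentence (though the 2a list has no 4-week visit). Nor are the 3- and 6-month scores the only evidence on lasting benefit: experimental therapy ends at 2 weeks, so the SAP's 1-month score and the 6-8 week visit in 2a also come after it.

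**What to change.** - Reconcile protocol sections 2a, 2g, 6c and 6e-iv so that every randomised patient has study assessments at 3 and 6 months whatever their symptoms or response. Confine the severity clause to additional clinical visits.
- Collect SNOT-22 by telephone or electronically from patients who do not attend.
- Report the number assessed by arm and visit.
- In the SAP, analyse late scores with a likelihood-based repeated-measures model that uses baseline and earlier scores. This handles attendance driven by earlier observed scores (step 4). Add a missing-not-at-random sensitivity analysis for attendance driven by the unseen late score (step 3).

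The cost is protocol wording, reminder contacts and some analysis time; the visits are already in the 2a schedule. The small downside is that Lund-Kennedy stays missing for those assessed only remotely. The SAP is written in the past tense. If collection is already complete, the first two changes come too late, but the counts by arm and visit would show how far late scores are missing and whether this differs by arm, and the revised analysis can still be done.
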